12.8.1 Disease Parameters

12.8.1.1 Measurable disease: A measurable node must have an LDi (longest diameter) greater than 1.5 cm. A measurable extranodal lesion should

have an LDi greater than 1.0 cm. All tumor measurements must be recorded in millimeters (or decimal fractions of centimeters).

12.8.1.2 Non-measured disease: All other lesions (including nodal, extranodal, and assessable disease) should be followed as nonmeasured disease (e.g., cutaneous, GI, bone, spleen, liver, kidneys, pleural or pericardial effusions, ascites).

12.8.1.3 Target lesions: For patients staged with CT, up to six of the largest target nodes, nodal masses, or other lymphomatous lesions that are measurable in two diameters (longest diameter [LDi] and shortest diameter) should be identified from different body regions representative of the patient's overall disease burden and include mediastinal and retroperitoneal disease, if involved.

12.8.2 Evaluation of Measurable Disease

Complete Response (CR)

Disappearance of all disease. CT or MRI should be free of residual mass or evidence of new disease. FDG-PET should be negative.

Complete Response Unconfirmed (CRu)

Residual mass is negative by FDG-PET; no new lesions by imaging examination; no new and/or progressive disease elsewhere

Partial Response (PR)

50% decrease in SPD (the sum of the products of the largest diameter and the perpendicular diameter for a tumor mass) on CT or MRI; FDG-PET may be positive (Deauville score or 4 or 5 with reduced lesional uptake compared with baseline); no new and/or PD; morphologic evidence of disease may be present in BM if present at diagnosis; however, there should be 50% reduction in percentage of lymphoma cells.

No Response (Stable Disease)

Neither sufficient shrinkage to qualify for PR nor sufficient increase to qualify for PD, taking as reference the smallest sum diameters while on study.

Progressive disease

For those with > 25% increase in SPD on CT or MRI, Deauville score 4 or 5 on FDG-PET with increase in lesional uptake from baseline, or development of new morphologic evidence of disease in BM

12.8.3 Evaluation of Non-measured Lesions (CT-based response, PET/CT based response not applicable)⁶⁴

Complete Response (CR): Absent non-measured lesions.

Partial response (PR): Absent/normal, regressed, lesions, but no increase.

Stable Disease (SD): No increase consistent with progression

Progressive Disease (PD): New or clear progression of preexisting non-measured lesions.

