This subprotocol is a component of the NCI-COG Pediatric MATCH trial APEC1621. The APEC1621SC screening protocol details the process used to identify actionable mutations in patient tumor samples which will determine eligibility for this subprotocol. This is a Phase 2 trial of LY3023414 in children with recurrent or refractory solid tumors, CNS tumors, and non-Hodgkin lymphomas harboring specified activating mutations of the PI3K/MTOR pathway. LY3023414 is a potent orally bioavailable small molecule inhibitor of class 1 PI3K isoforms, MTOR, and DNAPK. LY3023414 will be given twice daily continuously for 28-day cycles. Because the pediatric dose of LY3023414 has not been established, there will be a limited dose finding phase consisting of the first 12 evaluable patients enrolled on study. The primary endpoint will be objective response rate as determined by RECIST. Progression free survival (PFS) will be assessed as a secondary endpoint. In addition, toxicity will be assessed and the pharmacokinetics of LY3023414 in children will be evaluated.

EXPERIMENTAL DESIGN SCHEMA

Day 1-28	Day 28
LY3023414 (BID)	Evaluation

Patients will receive LY3023414 twice daily for 28-day cycles. Evaluations will occur at the end of every other cycle.

Therapy will be discontinued if there is evidence of progressive disease or drug related dose-limiting toxicity that requires removal from therapy ([Section 6.0](#)). Therapy may otherwise continue for up to 6 cycles (approximately 6 months) provided the patient meets the criteria for starting subsequent cycles ([Section 5.2](#)) and does not meet any of the criteria for removal from protocol therapy criteria ([Section 10.0](#)).

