³ If patients develop Grade 4 neutropenia then CBCs should be checked every 3 to 4 days until recovery to Grade 3

^{4A} Neurological exam also required for CNS patients.

- ⁴ Tumor Disease Evaluation should be obtained on the next consecutive cycle after initial documentation of either a PR or CR. Subsequent scans may restart 2 cycles after the confirmatory scan. If the institutional investigator determines that the patient has progressed based on clinical or laboratory evidence, he/she may opt not to confirm this finding radiographically.
- ⁵ Bone marrow aspirate and/or biopsy only required in patients suspected of having bone marrow metastasis on the basis of history, symptoms, laboratory evaluation or other clinical data.
- ⁶ Bone marrow aspirate and/or biopsy should only be performed on patients with known bone marrow involvement at baseline
- ⁷ Patient diary (see [Appendix III](#)) should be reviewed after completion of each treatment cycle and uploaded into RAVE.
- ⁸ See [Section 8.3](#) for details of PK studies.
- ⁹ With consent, two samples will be collected on this protocol (cycle 5 Day 1; and for patients receiving ≥ 5 cycles only: at progression or end of protocol therapy) see [Section 8.4](#) for details of the ctDNA studies. Note that a ctDNA sample is scheduled to be obtained on the APEC1621SC screening protocol prior to the initiation of treatment on this subprotocol.

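### The lymphoma partial-response rule in 12.8.2 ties residual marrow disease to diagnosis, not study baseline, and gives its 50% marrow reduction no reference point

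*Combined protocol and SAP*

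**What the plan says.** Objective response rate is the primary endpoint (1.1.1). As of Amendment 5A, one pooled cohort of 20 evaluable patients is judged by a rule of at least 3 responses (11.3.1). The opening summary and Section 2.5 describe the population as "children with recurrent or refractory solid tumors, CNS tumors, and non-Hodgkin lymphomas". Section 4.1.7.1.b admits patients with known marrow disease if their blood counts qualify.

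The PR rule for lymphoma and histiocytosis in 12.8.2 has this marrow clause: "morphologic evidence of disease may be present in BM if present at diagnosis; however, there should be 50% reduction in percentage of lymphoma cells". It has two parts:

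- Residual disease is tolerated conditionally, by reference to diagnosis.
- A reduction is required. No time point is attached to it.

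For PET, the same rule allows a positive scan "with reduced lesional uptake compared with baseline". It also requires "no new and/or PD". The progressive disease (PD) paragraph of 12.8.2 mentions marrow only as "development of new morphologic evidence of disease in BM".

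In 8.1, marrow is sampled before study when involvement is suspected. According to footnote 6, repeat samples "should only be performed on patients with known bone marrow involvement at baseline".

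**The concern.** In a relapsed or refractory population, diagnosis may lie well before study entry, with other treatment in between. Marrow status at the two times can differ. Only the change from the pre-treatment state says anything about LY3023414, so a response rule that looks back to diagnosis mixes the drug's effect with what happened before it.

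Two errors are possible. A patient whose marrow became involved after diagnosis could be refused PR despite a clear fall on drug. On one reading, a patient whose marrow was heavily involved at diagnosis could be credited with a reduction that earlier therapy produced. Either would enter the primary endpoint, where the threshold is only 3 responders.

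**Working it through.** **1. The plan's own figure.** From 11.3.1: n = 20, success at 3 or more responses, null rate 5%, target rate 25%. With P(X ≥ 3) = 1 − Σ C(20,i) pⁱ(1−p)²⁰⁻ⁱ for i = 0 to 2:

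- p = 0.25 gives 0.9087, against the stated power of 90%. Reproduced.
- p = 0.05 gives 0.0755. The stated 10% is thus a ceiling on alpha, not the attained level.

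No design figure is disputed. They serve only to size the effect below.

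**2. Reference points side by side.**

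- Solid tumours, PR (12.4.1): baseline sum of diameters.
- MIBG-positive neuroblastoma (12.5.3): score relative to the pre-treatment score; marrow by its state at enrolment.
- Neuroblastoma marrow (12.6.1): state at enrolment, with a numerical rule for a rise (a doubling, and at least 25% tumour).
- CNS tumours, PR (12.7.4): initial baseline measurements.
- Lymphoma, PR (12.8.2): PET against baseline; residual marrow against diagnosis; the 50% marrow reduction against nothing stated.

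Nothing in the documents defines diagnosis as study baseline.

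**3. The clause applied to cases.** The marrow percentages are invented for illustration, in the order diagnosis / study entry / on study. Assume that the sum of products of diameters has fallen enough for PR (for example by 60%).

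- 0 / 40 / 10: the fall from entry is 1 − 10/40 = 75%. Disease remains in the marrow and was not there at diagnosis, so the literal rule refuses PR. No other section restores it.
- 0 / 40 / 0: the marrow has cleared, so the clause does not stand in the way.
- 80 / 10 / 30: measured from diagnosis the reduction is 1 − 30/80 = 62.5%, and the clause is met. Measured from entry the marrow has risen threefold (30/10), and the clause fails.

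**4. Is the third case PD in any event?** PR is barred if there is PD. The PD paragraph of 12.8.2 covers only new marrow disease, which this is not. Two other provisions might catch it:

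- 12.2 counts progression in any established lesion as PD, whatever happens elsewhere. It speaks of lesions and gives no marrow threshold.
- 12.8.3 counts clear worsening of existing non-measured disease as PD. Its heading limits it to CT-based response, and the examples of non-measured disease in 12.8.1.2 do not name marrow, although that definition is broad.

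The text does not settle whether either applies to marrow.

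**5. Size, if one such patient exists.** The documents give no count of marrow-involved lymphoma or histiocytosis patients; 0 to 1 of 20 is an assumption. A miscoded patient decides the result when exactly 2 of the other 19 respond: P(X = 2) = C(19,2) p²(1−p)¹⁷ = 171 p²(1−p)¹⁷.

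- p = 0.05: 0.179
- p = 0.10: 0.285
- p = 0.25: 0.080

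In terms of error rates:

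- One certain false PR raises the chance of success at a 5% true rate from 0.0755 to P(X ≥ 2 | n = 19) = 0.2453.
- One patient who can never be scored PR lowers power at 25% from 0.9087 to P(X ≥ 3 | n = 19) = 0.8887.

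The two sets of figures agree: 0.179 × 0.95 ≈ 0.170 = 0.2453 − 0.0755, and 0.080 × 0.25 = 0.020 = 0.9087 − 0.8887.

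**The case against.** The best defence is that *diagnosis* is loose wording for the pre-treatment state. The protocol never says initial diagnosis. Section 12.3.3.7, on the same lymphoma criteria, also speaks of a positive PET scan at diagnosis when it means following response on trial, which makes sense only against the pre-treatment scan. Section 12.9.1 counts best response from the start of treatment. This has weight: a sensible reader may well apply baseline, and the two words cannot be said never to be interchangeable here. But the same PR rule uses baseline for PET, and no definition equates the terms, so the assessor has to guess.

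A reader might infer that 12.8.2 lets a marrow that worsens on study count as PR. The documents do not support that as a settled outcome. The word *diagnosis* governs whether residual disease may be present; the 50% reduction has no reference of its own. The fall in the sum of products in the same rule also lacks one and would naturally be read as change on study. Even if the marrow reduction is read against diagnosis, the no-PD condition together with 12.2 or 12.8.3 may exclude PR. That part of the objection stands, and the point is only an ambiguity.

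The objection that few patients can be affected also stands. The literal refusal of PR needs measurable lymphoma or histiocytosis, marrow clear at diagnosis, marrow involved at entry, incomplete clearance on study, and otherwise sufficient and confirmed shrinkage.

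**Conclusion.** The point holds in limited form. On the literal text, a patient with marrow negative at diagnosis, positive at entry and still positive but at least halved on drug cannot be scored PR. Nothing elsewhere in the protocol corrects this. Separately, the 50% reduction lacks a reference point, and the class of a rise in already involved marrow is unsettled between 12.8.2, 12.2 and 12.8.3.

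It would be too strong to say that every responder with marrow relapse is shut out. Patients whose marrow clears, or whose marrow was also involved at diagnosis, can still be PR.

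The probabilities of 18%, 29% and 8% are conditional on one miscoded patient being in the cohort. With 0 to 1 such patients assumed among 20, the expected effect is small, and the design's alpha and power do not change. The reason to act is that this is a stated rule for the primary endpoint that departs from the protocol's other response rules, and that one patient can matter when the threshold is 3.

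**What to change.** Make three changes, all in wording:

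- In the PR paragraph of 12.8.2, replace the reference to diagnosis with study baseline, meaning the pre-study marrow in 8.1.
- State in the same clause that the 50% reduction is measured from the study-baseline marrow percentage.
- Reconcile the PD paragraph of 12.8.2 with 12.2 and 12.8.3, so that the text says how a rise in already involved marrow is classed. Which class applies is for the study team to decide.

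The cost is a few words. Section 8.1 already schedules marrow before study where involvement is suspected, and every other cycle in patients with involvement at baseline, so no new procedure is needed. Any lymphoma or histiocytosis patient already enrolled with marrow disease should be checked once against the clarified rule.

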12.8.4 Evaluation of organ enlargement⁶⁴

Complete Response (CR): Regress to normal

Partial response (PR): Spleen must have regressed by >50% in length beyond normal

Stable Disease (SD): No increase consistent with progression

Progressive Disease (PD): In the setting of splenomegaly, the splenic length must increase by 50% of the extent of its prior increase beyond baseline. If no prior splenomegaly, must increase by at least 2 cm from baseline.

New or recurrent splenomegaly

12.9 **Best Response**

Two objective status determinations of disease status, obtained on two consecutive determinations, separated by at least a 3 week time period, are required to determine the patient's overall best response. Two objective status determinations of CR before progression are required for best response of CR. Two determinations of PR or better before progression, but not qualifying for a CR, are required for a best response of PR. Two determinations of stable/no response or better before progression, but not qualifying as CR or PR, are required for a best response of stable/no response; if the first objective status is unknown, only one such determination is required. Patients with an objective status of progression on or before the second evaluations (the first evaluation is the first radiographic evaluation after treatment has been administered) will have a best response of progressive disease. Best response is unknown if the patient does not qualify for a best response of progressive disease and if all objective statuses after the first determination and before progression are unknown.

12.9.1 Evaluation of Best Overall Response

The best overall response is the best response recorded from the start of the treatment until disease progression/recurrence (taking as reference for progressive disease the smallest measurements recorded since the treatment started). The patient's best response assignment will depend on the achievement of both measurement and confirmation criteria.

Table 5. Sequences of overall response assessments with corresponding best response.

1 st Assessment	2 nd Assessment	Best Response
Progression		Progressive disease
Stable, PR, CR	Progression	Progressive disease
Stable	Stable	Stable
Stable	PR, CR	Stable
Stable	Not done	Not RECIST classifiable

PR	PR	PR
PR	CR	PR
PR, CR	Not done	Not RECIST classifiable
CR	CR	CR

12.9.2 Duration of Response

Duration of overall response: The duration of overall response is measured from the time measurement criteria are met for CR or PR (whichever is first recorded) until the first date that recurrent or progressive disease is objectively documented (taking as reference for progressive disease the smallest measurements recorded since the treatment started).

The duration of overall CR is measured from the time measurement criteria are first met for CR until the first date that progressive disease is objectively documented.

Duration of stable disease: Stable disease is measured from the start of the treatment until the criteria for progression are met, taking as reference the smallest measurements recorded since the treatment started, including the baseline measurements.

13.0 ADVERSE EVENT REPORTING REQUIREMENTS

Adverse event data collection and reporting which are required as part of every clinical trial, are done to ensure the safety of patients enrolled in the studies as well as those who will enroll in future studies using similar agents. Adverse events are reported in a routine manner at scheduled times during a trial. (Please follow directions for routine reporting provided in the Case Report Forms for this protocol). Additionally, certain adverse events must be reported in an expedited manner to allow for optimal monitoring of patient safety and care. The following sections provide information about expedited reporting.

Reporting requirements may include the following considerations: 1) whether the patient has received an investigational agent; 2) whether the adverse event is considered serious; 3) the grade (severity); and 4) whether or not hospitalization or prolongation of hospitalization was associated with the event.

An investigational agent is a protocol drug administered under an Investigational New Drug Application (IND). In some instances, the investigational agent may be available commercially, but is actually being tested for indications not included in the approved package label.

13.1 Expedited Reporting Requirements – Serious Adverse Events (SAEs)

Any AE that is serious qualifies for expedited reporting. An AE is defined as any untoward medical occurrence associated with the use of a drug in humans, whether or not considered drug related. A Serious Adverse Event (SAE) is any adverse drug event (experience) occurring at any dose that results in ANY of the following outcomes:

- 1) Death.
- 2) A life-threatening adverse drug experience.
- 3) An adverse event resulting in inpatient hospitalization or prolongation of existing hospitalization (for \geq 24 hours). This does not include hospitalizations that are part of routine medical practice.
- 4) A persistent or significant incapacity or substantial disruption of the ability to conduct normal life functions.
- 5) A congenital anomaly/birth defect.
- 6) Important Medical Events (IME) that may not result in death, be life threatening, or require hospitalization may be considered a serious adverse drug experience when, based upon medical judgment, they may jeopardize the patient or subject and may require medical or surgical intervention to prevent one of the outcomes listed in this definition.

13.1.1 Reporting Requirements - Investigator Responsibility

Clinical investigators in the treating institutions and ultimately the Study Chair have the primary responsibility for AE identification, documentation, grading, and assignment of attribution to the investigational agent/intervention. It is the responsibility of the treating physician to supply the medical documentation needed to support the expedited AE reports in a timely manner.

Any medical documentation supporting an expedited report (eg, H & P, admission and/or notes, consultations, ECG results, etc.) MUST be faxed within 48-72 hours to the NCI. NOTE: English is required for supporting documentation submitted to the numbers listed below in order for the NCI to

meet the regulatory reporting timelines.

Fax supporting documentation for AEs related to investigational agents supplied under a CTEP IND to: **PPD**

Also: Fax or email supporting documentation to COG for **all** IND studies ([contact]; email: [contact]; Attention: COG AERS Coordinator).

- **ALWAYS include the ticket number on all faxed documents.**
- **Use the NCI protocol number and the protocol-specific patient ID provided during trial registration on all reports.**

13.1.2 CTEP-AERS Expedited Reporting Methods

Expedited AE reporting for this study must only use CTEP-AERS (Adverse Event Expedited Reporting System), accessed via the CTEP home page <https://eapps-ctep.nci.nih.gov/ctepaers>.

Send supporting documentation to the NCI by fax ([contact]) and by email to the APEC1621D COG Study Assigned Research Coordinator and [contact]; Attention: COG AERS Coordinator. **ALWAYS include the ticket number on all faxed and emailed documents.**

13.2 Steps to Determine If an Adverse Event Is To Be Reported In an Expedited Manner

Step 1: Identify the type of adverse event using the current version of the NCI CTCAE V 5.0. The descriptions and grading scales found in the current version of the CTCAE V 5.0 will be used for AE reporting. All appropriate treatment areas should have access to a copy of the CTCAE v5.0. A copy of the CTCAE v5.0 can be downloaded from the CTEP website (<http://ctep.cancer.gov>).

Step 2: Grade the adverse event using the NCI CTCAE v5.0.

Step 3: Review Table A in this section to determine if:

- the adverse event is considered serious;
- there are any protocol-specific requirements for expedited reporting of specific adverse events that require special monitoring; and/or
- there are any protocol-specific exceptions to the reporting requirements.

- Any medical event equivalent to CTCAE v5.0 grade 3, 4, or 5 that precipitates hospitalization (or prolongation of existing hospitalization) must be reported regardless of attribution and designation as expected or unexpected with the exception of any events identified as protocol-specific expedited adverse event reporting exclusions.
- Any event that results in persistent or significant disabilities/incapacities, congenital anomalies, or birth defects must be reported via CTEP-AERS if the event occurs following treatment with an agent under a CTEP IND.
- Use the NCI protocol number and the protocol-specific patient ID provided during trial registration on all reports.
- As referenced in the CTEP Adverse Events Reporting Requirements, an AE that resolves and then recurs during a subsequent cycle does not require CTEP-AERS

reporting unless (1) the Grade increases; or (2) hospitalization is associated with the recurring AE.

- Some adverse events require notification **within 24 hours** (refer to Table A) to NCI via the web at <http://ctep.cancer.gov> (telephone CTEP at: **[contact]** within 24 hours of becoming aware of the event if the CTEP-AERS 24-Hour Notification web-based application is unavailable). Once internet connectivity is restored, a 24-hour notification phoned in must be entered electronically into CTEP-AERS by the original submitter at the site.
- When the adverse event requires expedited reporting, submit the report within 5 or 7 calendar days of learning of the event (refer to [Table A](#)).

Table A: Phase 1 and Early Phase 2 Studies: Expedited Reporting Requirements for Adverse Events that Occur on Studies under an IND/IDE within 30 Days of the Last Administration of the Investigational Agent/Intervention ^{1,2}

FDA REPORTING REQUIREMENTS FOR SERIOUS ADVERSE EVENTS (21 CFR Part 312)

NOTE: Investigators **MUST** immediately report to the sponsor **ANY** Serious Adverse Events, whether or not they are considered related to the investigational agent(s)/intervention (21 CFR 312.64)

An adverse event is considered serious if it results in **ANY** of the following outcomes:

- 1) Death
- 2) A life-threatening adverse event
- 3) An adverse event that results in inpatient hospitalization or prolongation of existing hospitalization for ≥ 24 hours
- 4) A persistent or significant incapacity or substantial disruption of the ability to conduct normal life functions
- 5) A congenital anomaly/birth defect.
- 6) Important Medical Events (IME) that may not result in death, be life threatening, or require hospitalization may be considered serious when, based upon medical judgment, they may jeopardize the patient or subject and may require medical or surgical intervention to prevent one of the outcomes listed in this definition. (FDA, 21 CFR 312.32; ICH E2A and ICH E6).

ALL SERIOUS adverse events that meet the above criteria **MUST** be immediately reported via CTEP-AERS within the timeframes detailed in the table below.

Hospitalization	Grade 1 and Grade 2 Timeframes	Grade 3-5 Timeframes
Resulting in Hospitalization ≥ 24 hrs	7 Calendar Days	24-Hour 5 Calendar Days
Not resulting in Hospitalization ≥ 24 hrs	Not required	

NOTE: Protocol specific exceptions to expedited reporting of serious adverse events are found in the Specific Protocol Exceptions to Expedited Reporting (SPEER) portion of the CAEPR.

Expedited AE reporting timelines are defined as:

- o “24-Hour; 5 Calendar Days” - The AE must initially be reported via CTEP-AERS within 24 hours of learning of the AE, followed by a complete expedited report within 5 calendar days of the initial 24-hour report.
- o “7 Calendar Days” - A complete expedited report on the AE must be submitted within 7 calendar days of learning of the AE.

¹Serious adverse events that occur more than 30 days after the last administration of investigational agent/intervention and have an attribution of possible, probable, or definite require reporting as follows:

Expedited 24-hour notification followed by complete report within 5 calendar days for:

- All Grade 3, 4, and Grade 5 AEs

Expedited 7 calendar day reports for:

- Grade 2 AEs resulting in hospitalization or prolongation of hospitalization

² For studies using PET or SPECT IND agents, the AE reporting period is limited to 10 radioactive half-lives, rounded UP to the nearest whole day, after the agent/intervention was last administered. Footnote "1" above applies after this reporting period.

Effective Date: May 5, 2011

13.3 Exceptions to CTEP-AERS Expedited Reporting Requirements:

- Myelosuppression, (Grade 1 through Grade 4 adverse events as defined in the table below), does not require expedited reporting, unless it is associated with hospitalization.

Category	Adverse Events
INVESTIGATIONS	Platelet count decreased
INVESTIGATIONS	White blood cell decreased
INVESTIGATIONS	Neutrophil count decreased
INVESTIGATIONS	Lymphocyte count decreased
BLOOD/LYMPHATICS DISORDERS	Anemia

- Grade 1 and 2 adverse events listed in the table below do **not** require expedited reporting via CTEP-AERS, unless it is associated with hospitalization.

Category	Adverse Events
GASTROINTESTINAL DISORDERS	Constipation
GASTROINTESTINAL DISORDERS	Oral dysesthesia
INVESTIGATIONS	Alanine aminotransferase increased
INVESTIGATIONS	Creatinine increased
INVESTIGATIONS	Weight Loss
METABOLISM AND NUTRITION DISORDERS	Hyperglycemia
NERVOUS SYSTEM DISORDERS	Headache
NERVOUS SYSTEM DISORDERS	Paresthesia
RESPIRATORY, THORACIC AND MEDIASTINAL DISORDERS	Dyspnea
SKIN AND SUBCUTANEOUS TISSUE DISORDERS	Dry skin
SKIN AND SUBCUTANEOUS TISSUE DISORDERS	Pruritus

- See also the Specific Protocol Exceptions to Expedited Reporting (SPEER) in [Section 9.1.8](#) of the protocol.

